#### **Development and Validation of a Survival Outcome Prediction Algorithm for Patients Evaluated for Advanced Heart Failure Therapies (Study 1). Clinical Prediction Model Development (n=96).**

First, we aimed to understand the relationship of clinical information with patients' post-surgical outcomes. A retrospective study was conducted in 96 advanced heart failure patients undergoing mechanical circulatory support (MCS) surgery from 2012 to 2016 in a tertiary academic medical center. Clinical data was collected one day before and one year after MCS implantation. Twelve clinically established prognostic variables(107, 117-131) were selected, including serum bilirubin, serum creatinine, blood glucose, white blood cell count, alveolar oxygen pressure, fraction of inspired oxygen, systolic and diastolic blood pressures, International Normalized Ratio, heart rate, respiratory rate, temperature, and the Glasgow Coma Scale. We calculated Sequential Organ Failure Assessment (SOFA)(105) and Model for End Stage Liver Disease Except-INR (MELD-XI) scores(106). We also included chronological age as an important demographic parameter, which has been shown to correlate with immune system function, and overall health and survival(132-134). Of 12 variables included in our clinical prediction model, age showed the highest correlation with patients' outcome after surgery, followed by respiratory rate, white blood cell count, and minimum diastolic blood pressure (**Table 4**)(135-137). **Gene Discovery on Single-Intervention (MCS) Cohort (n=29).** Next, we conducted a study with 29 patients undergoing MCS surgery from 2012 to 2014. PBMC samples were collected one day before surgery (day -1). Clinical data was collected on day -1, day 8 and one year postoperatively. Patients were classified by SOFA and MELD-XI scores into improving (both scores improved from day -1 to day 8, n=17) and not improving (either one or both scores did not improve from day -1

Parameter	Estimate	Std. Error	t value	Pr (> t )
Age	-0.0068	0.0027	-2.540	0.012
SOFA Score	-0.0141	0.0189	-0.744	0.4578
GCS	0.1874	0.3366	0.557	0.5785
Temperature	0.0037	0.0610	0.061	0.9514
Resp. Rate	-0.2517	0.1277	-1.972	0.0503
Bilirubin	-0.0608	0.0398	-1.527	0.1286
WBC	-0.1456	0.0726	-2.005	0.0467
Glucose	0.0011	0.0009	1.137	0.257
Heart Rate	0.0016	0.0020	0.815	0.4165
Max. Systolic	-0.0003	0.0022	-0.128	0.8984
Min. Diastolic	0.0046	0.0027	1.732	0.0851
INR	0.0561	0.0478	1.173	0.2426

**Table 4.** Twelve clinically established prognostic variables. Gray indicates four parameters; p-value <0.10 used for model development.

to day 8, n=12). RNA sequencing was performed on purified mRNA and analyzed using Next Generation Sequencing (NGS) Strand. Differentially expressed genes were identified by Mann-Whitney test with Benjamini-Hochberg false discovery rate (FDR) correction. Preoperative differentially expressed genes were used to construct a support vector machine algorithm to predict improving vs. non-improving membership. Out of 28 patients alive 8 days postoperatively, one-year survival was 88% in the improving group and 27% in the non-improving group. We identified 28 preoperative differentially expressed genes between groups, with an average 93% prediction accuracy of group membership. Out of 105 genes identified preoperatively between one-year survivors and non-survivors, 12 genes overlapped with the 28 predictive genes (*AGRN*, *SAP25*, *ANKRD22*, *BATF2*, *FRMD6*, *HEXA-AS1*, *DNM1P46*, *NAPSA*, *KIR2DL4*, *RHBDD3*, *TIMP3*, and *BCORP1*). These predictive genes are all implicated in inflammation and immune system regulation (138-162). The 12 genes and 4 clinical parameters are summarized in **Table 5**. The 12 genes demonstrated similar gene expression

**Figure 3.** Average gene expression profiles of 12

Parameter		Average of Survivors (n=18)	Average of Non-Survivors (n=11)	Description
Transcriptomic Data	BCORP1	-0.22±2.25	0.64±1.61	BCORP1 is a pseudogene. Although not fully functional, pseudogenes may be functional, similar to other kinds of noncoding DNA, which can perform regulatory functions.
	BATF2	-1.24±1.41	-0.19±0.86	BATF2 belongs to a class of transcription factors that regulate various immunological functions and control the development and differentiation of immune cells. BATF2 controls Th2 cell functions and lineage development of T lymphocytes. Following infection, BATF2 participates in the development of and differentiation of CD8+ thymic conventional dendritic cells. BATF2 is involved in IFN signaling and positive regulation of immune responses by altering expression of cytokines and chemokines.
	FRMD6	-0.81±1.10	-0.81±1.10	FRMD6 has been linked to various complex diseases, such as asthma, Alzheimer's disease, lung cancer, and colorectal cancer. It regulates cell proliferation and apoptosis and is thought to have tumor suppressor properties. FRMD6 mediates Vitamin D inhibition of immune cell proliferation.
	KIR2DL4	-0.63±1.73	0.62±1.13	KIR2DL4 codes for transmembrane glycoproteins expressed by natural killer (NK) cells and subsets of T cells. KIR2DL4 inhibits the NK cell activity and reduces T cell death in Sezary syndrome. KIR2DL4 recognizes human leukocyte antigen G and has been suggested as a useful diagnostic biomarker of neoplastic NK-cell proliferations.
	HEXA-AS1	0.46±0.85	-0.75±1.21	HEXA-AS1 is an antisense RNA Gene and is affiliated with the lncRNA class. Diseases associated with HEXA-AS1 include Tay-Sachs Disease.
	DNM1P46	-1.25±1.09	0.58±1.37	DNM1P46 is a pseudogene associated with diagnosing, treating, and monitoring chronic inflammatory response syndrome. DNM1P46 is a long noncoding RNA that is mediated by p53, a gene that codes for a protein that regulates the cell cycle and hence functions as a tumor suppression. p53 was activated in DNM1P46 during apoptotic pathways.
	RHBDD3	0.24±1.28	-1.43±1.19	RHBDD3 is a member of the rhomboid family of proteases that suppresses the activation of dendritic cells (DCs) and production of interleukin 6 (IL-6) triggered by Toll-like receptors. The rhomboid proteins are involved in signaling via the receptor for epidermal growth factor, mitochondrial homeostasis and parasite invasio. RHBDD3 negatively controls the activation of DCs and maintains the balance of regulatory T cells and TH17 cells by inhibiting the production of IL-6 by DCs, thus contributing to the prevention of autoimmune diseases.
	SAP25	0.79 ± 1.05	-0.59±1.13	SAP25 is a member of the nucleocytoplasmic shuttling proteins that are located in promyelocytic leukemia nuclear bodies. Promyelocytic leukemia nuclear bodies are implicated in diverse cellular functions, such as gene regulation, apoptosis, senescence, DNA repair, and antiviral response.
	NAPSA	0.51±1.16	-0.35±1.06	NAPSA is a pronapsin gene, which may have a considerable diagnostic value as a marker for primary lung cancer. NAPSA was detected in a subset of poorly differentiated papillary thyroid carcinomas and anaplastic carcinomas.
	TIMP3	0.58±1.40	-0.60±1.01	TIMP3 is an extracellular matrix-bound protein, which regulates matrix composition and affects tumor growth. TIMP3 suppresses tumor inactivation in cancer by mechanisms of invasion and angiogenesis. TIMP-3 downregulation is associated with aggressive non-small cell lung cancer and hepatocarcinoma cells, as compared with less invasive or normal lung and liver cells. It mediates VEGF by blocking the binding of VEGF to VEGF receptor-2, inhibiting downstream signaling, and prevents angiogenesis. These inhibitive properties seem to be independent of its matrix metalloproteinases-inhibitory activity.
	AGRN	-1.81±1.52	0.17±0.60	AGRN is evolutionarily conserved in the extracellular matrix. Its intracellular processes include proliferation, apoptosis, migration, motility, autophagy, angiogenesis, tumorigenesis, and immunological responses. AGRN interacts with the α/β-dystroglycan receptor in the formation of immunological synapses with lymphocytes and aids in activation and maintenance of monocyte cell survival downstream in an α-dystroglycan dependent manner. The AGRN LG3 domain has been used as a biomarker for detection of prematurely ruptured fetal membranes.
	ANKRD22	-0.81±1.87	0.17±0.49	ANKRD22, involved in protein lipid modification, has been patented as a possible biomarker for several types of cancers to identify patient responses to cancer immunotherapy.
Clinical Data	Age	54±15	61±14	Age is associated with immune system function, overall health and survival.
	Min. DBP	49±8	51±13	Minimum diastolic blood pressure has been shown to have an inverse relationship with mortality rates in patients ages ≥85 years old.
	WBC	11.19±4.21	11.01±4.40	Total white blood cell count is a prognostic indicator of long-term survival, reflects immune system inflammatory activation, and may indicate progressive multi organ dysfunction.
	Resp. Rate	20±4	23±5	Respiratory rate serves as a key marker in patients experiencing sepsis or systemic inflammation.

**Table 5.** 12 genes and 4 clinical parameters used in preliminary model development.

within short-term recovery and one-year survivor groups and were consistently differentially expressed between both groups. Average gene expression profiles are displayed in **Figure 3**. We concluded that in advanced heart failure patients following MCS implantation, preoperative gene expression profiling predicts early changes in organ function scores and correlates with long-term outcomes and gene expression lends itself to outcome prediction(90). The 12, 28, and 105 gene lists have been patented by UCLA. **Algorithm Prototype Development.** Based on these data, we constructed a prototype algorithm to convert gene expression values of the 12 genes and 4 clinical parameters into a numerical survival prediction estimate. The algorithm is written as follows: 
$$P = \frac{e^{(\beta + \alpha_1 X_1 + \dots \alpha_n X_n)}}{1 + e^{(\beta + \alpha_1 X_1 + \dots \alpha_n X_n)}}$$
,  $\beta$  and  $\alpha$  estimates were

calculated using a LASSO logistic regression model(163). Youden's index was used to establish a cutoff point at 0.749, with values >0.749 predicting survivor status and ≤0.749 predicting non-survivor status. **Predictive Power on Independent Cohort Undergoing Various Advanced Heart Failure Therapies (n=48).** Next, we validated the predictive accuracy of the prototype algorithm that contains the previously identified 12 genes and 4 clinical parameters, in independent samples from advanced heart failure patients undergoing various therapies (n=48, including guidelines-directed medical therapy, heart transplant, MCS, and transcatheter aortic valve replacement). Performance characteristics for the algorithm on the independent cohort are summarized in **Table 6**. On this larger, more heterogeneous cohort, our test had 71% sensitivity, 90% specificity, 56% positive predictive value, and 95% negative predictive value. **Test Performance on Stage 1 Proof-of-Concept Pooled Cohort (n=77).** Next, we pooled the 29 patients used for gene selection with the 48 patients undergoing various advanced heart failure therapies to perform the following analysis (**Table 7**). One-year survival was 77% (59/77) in this combined cohort. ComBat was used for batch effect correction(164-166). Univariate analysis between 1-year survival status and the 12, 28, and 105 gene lists confirmed that all significantly differentially expressed genes in this combined cohort exhibited the same directionality as in the original cohort used for initial gene discovery(90). Various logistic regression models were constructed using the LASSO method(163) and measures of predictive performance such as AUCs are summarized in **Table 8**. Prediction of 1-year survival using 4 clinical parameters alone (age, white blood cell count, respiratory rate, and minimum diastolic blood pressure) achieved an AUC=0.69. Adding the 12-gene candidates to the clinical model without ComBat correction improved the 1-year survival prediction to AUC=0.90. The 12-gene list with ComBat correction and clinical data led to an observed AUC=0.86. We concluded that: 1) the direction of gene expression in the pooled 77 patient cohort was similar to that of the original 29 patients used for gene discovery, 2) batch effects played a minor role in data performance and 3) the addition of 12 genes meaningfully improved 1-year survival prediction of outcomes in patients undergoing diverse advanced heart failure therapies compared to the clinical model alone. **Prototype Score Construction (n=77).** Next, from the prototype raw numerical survival prediction algorithm score, we calculated a prototype clinical score for each of the 77 patients using non-batch adjusted data and risk stratified into 5 quintiles (**Table 9**). Note that, consistent with the UCLA patent application language guided by the intended clinical use, higher prototype raw scores translate into higher clinical scores. Higher deciles indicated binning of higher clinical scores and a higher likelihood of 1-year survival post-advanced heart failure therapy. The pooled survival rate for the top 6 deciles was 0.96 (47/49), and the survival rate for the pooled lower 4 deciles was 0.43 (12/28).

**Multi-Omics Analysis of Exercise-Induced Changes in Health and Heart Failure (Study 2).** In order to assess the relationship between cf-mtDNA and the PBMC transcriptome, PBMC immunophenotypes, cytokines and clinical exercise physiology parameters in health and disease, we characterized the temporal dynamics of the immune system under exercise and resting conditions in healthy volunteers (n=4) and patients with heart failure (n=16). We performed integrated analysis of genomic, transcriptomic, and proteomic data, as well as

Cut Off 0.749 (Youden's Index)	29 Patients (Gene Discovery)	48 Patients (Independent Validation)
Sensitivity	100%	71%
Specificity	72%	90%
Positive Pred. Value	69%	56%
Negative Pred. Value	100%	95%

**Table 6.** Performance characteristics of prototype test.

	Total (n=77)	1-Year Survivors (n=59)	Non-Survivors (n=18)	P-value
Age	56 (16)	54 (17)	63 (12)	0.037
SOFA Score	9.3 (3.4)	9.2 (3.2)	9.7 (4.0)	0.567
Male	64 (83.1%)	49 (83%)	15 (83.3%)	0.978
Procedure				0.124
GDMT	4 (5%)	3 (5%)	1 (6%)	
HTx	31 (40%)	28 (47%)	3 (17%)	
MCS	38 (49%)	25 (42%)	13 (72%)	
TAVR	4 (5%)	3 (5%)	1 (6%)	
WBC count	9.3 (3.7)	9.2 (3.8)	9.8 (3.4)	0.502
Resp. Rate	19.7 (5.8)	19.5 (5.9)	20.3 (5.5)	0.550
MELD-XI Score	13.9 (6.5)	13.5 (6.6)	15.3 (6.2)	0.300
Min. DBP	54.2 (12.5)	54.8 (12.0)	52.3 (14.1)	0.473

**Table 7.** Demographic data of 77 patients in Proof-of-Concept Study.

[figure not shown]
Model	AUC	% Increase in Accurate Survival Prediction
Clinical (age, WBC, RR, MDBP)	0.69	--
12 genes (raw) + clinical	0.90	68%
12 genes (COMBAT) + clinical	0.86	55%

**Table 8.** Modeling and test algorithm predictive performance on combined cohort

[figure not shown]
Outcome				Prototype Algorithm Score (1-10)
Quintile	Survivor	Non-Survivor	Total	
5	15	0	15	1.00
4	15	1	16	0.94
3	14	1	15	0.93
2	12	4	16	0.75
1	3	12	15	0.20
Total	59	18	77	0.77

**Table 9.** Predictive performance of risk-stratified deciles.

[figure not shown]
clinical data from the multivariate cardiopulmonary exercise panel. All participants underwent exercise testing. Blood samples were collected at 3 time-points: before (TP1), during (TP2), and 1-hour after peak oxygen uptake (VO2) (TP3). **Genome Data.** To understand the cfDNA dynamics during exercise testing, we performed total cfDNA as well as cf-mtDNA fragment quantification correlation analysis with VO2 max and percent predicted of VO2 max for all 20 participants at 3 timepoints (**Figure 4**). We observed a positive correlation between cardiorespiratory performance (as measured by peak VO2 and percent predicted of peak VO2) and cf-mtDNA at TP2. A negative correlation was found between cardiorespiratory performance and cf-mtDNA, beginning at the time of peak VO2 and more pronounced 1 hour after peak VO2. Numbers of cf-mtDNA fragments decreased after peak VO2 in healthy volunteers and increased in heart failure. Heart failure patients had pronounced cf-mtDNA fragments one hour after peak VO2. Numbers of cf-mtDNA fragments decreased after peak VO2 in healthy volunteers and increased in heart failure. **Transcriptome Data.** In both groups, a differential relationship was observed between cf-mtDNA fragment number and expression of 9 PBMC transcripts associated with reactive oxygen species (**Figure 5**). **Proteome Data.** A differential relationship was found between the reactive oxygen species related PBMC transcripts and pro-inflammatory cytokines of both groups (**Figure 6**). These preliminary data suggest that temporal dynamics of cf-mtDNA correlates with gene expression and cytokine production and that these patterns differ in healthy individuals and those with chronic disease.

**Figure 4.** Trends in VO2 max, % predicted VO2 max, and genomic data. Median number of cf-mtDNA fragments in healthy volunteers (HV, white boxplots) and heart failure (HF, grey boxplots).

**Figure 5.** Heat map of Pearson correlation of 9 differentially expressed genes involved in oxidative stress signalling by reactive oxygen species and fragment number of cell free mitochondrial DNA at timepoint 1, 2, and 3 in healthy volunteers (HV) and heart failure patients (HF).

**Figure 6.** Heat map of Pearson correlation of 9 differentially expressed genes involved in oxidative stress signaling by reactive oxygen species (from top to bottom: PARS2, DUSP2, CCR2, TNFAIP3, NFKBIA, PER1, FPR2, HSPA12B, and MAFF) and 10 differentially expressed cytokines (from left to right: FGF-2, G-CSF, fractalkine, MCP-3, IL-13, IL-17A, IL-1a, IL-4, IL-6, TNFb, and VEGF) at timepoint (TP) 1, 2, and 3 in healthy volunteers and heart failure patients.

## SPECIFIC AIMS

**AIM 1: CORRELATE MULTIOMIC DATA WITH OUTCOMES. Hypothesis and Objectives.** We hypothesize that various clinical COVID-19 disease outcome phenotypes correlate with molecular data and clinical patterns and are associated with immunologic pathways. Our first objective is to identify and confirm mono-dimensional genomic, transcriptomic, proteomic and clinical parameters that correlate with outcomes (Aim 1.1). Outcomes are defined as new onset or worsening frailty, single organ dysfunction, multiorgan dysfunction, and death within one year (primary endpoint) and at time of discharge (secondary endpoint). Since genomics, transcriptomics and proteomics often have complementary roles, our second objective is to perform multi-omics correlation analysis (Aim 1.2). Our third objective is to perform Weighted Gene Co-Expression Network Analysis (WGCNA) and pathway analysis to understand the role of the genes involved in the inflammatory response during SARS-CoV-2 infection (Aim 1.3).

**Aim 1.1: Single-omic identification of candidate genomic, transcriptomic, proteomic and clinical parameters that correlate with outcomes. Objective.** Our objective is to identify single-omic parameters (genomic, transcriptomic, proteomic) and clinical data that correlate with COVID-19 outcomes. We will perform exploratory analyses on the first 100 samples and confirm these parameters on the following 200 samples (**Figure 2**). **Genomic Analysis.** Raw cfDNA sequences will be aligned to HG38 and cf-mtDNA to HG38\_MT\_only (Strand NGS 3.3.1). ComBat will be used for batch effect correction(164-166). We will calculate the number of cf-mtDNA fragments in each sample. **Transcriptomic Analysis.** Raw transcriptome data will be aligned (HG19) and normalized (DESeq), batch effect corrected by ComBat(164-166) and filtered by expression (20th to 100th percentile) (Strand NGS (Avadis)). Differentially expressed genes between positive and negative endpoint groups will be identified by non-parametric statistics (Mann-Whitney test with Benjamini-Hochberg correction). We will use a more relaxed criteria of FDR=0.1 and fold change of at least 2.0 to identify significant genes as previously described by our group(90, 167, 168). **Immunophenotyping Analysis.** We will identify COVID-19

antigen exposed PBMC subsets for comparative analysis to genome, transcriptome and cytokine data. Analyses will be performed using the FCS Express V4 analysis software. **Cytokine Analysis.** The median fluorescent intensity data will be processed using a 5-parameter logistic fitting method to calculate cytokine concentrations by Milliplex analyst 3 software. We expect to achieve test results with 3-4% intra-plate coefficient of variation and less than 15% inter-plate coefficient of variation. **Interpretation of Results.** We expect COVID-19 patients with new onset or worsening frailty, organ dysfunction and death within one year to have more pronouncedly altered inflammatory profiles than patients who recover. We expect to find differentially expressed genes and differences in cf-mtDNA patterns, leukocyte subpopulations and cytokine production between patients with positive and negative endpoint outcomes.

**Aim 1.2: Multi-omics correlation analysis. Objective.** Genomics, transcriptomics and proteomics often have complementary roles to jointly perform a certain biological function and create a specific observable phenotype. Our objective in Aim 1.2 is to establish a correlation pattern between the multi-omics data and the outcome data in symptomatic COVID-19 patients. **Bioinformatics.** Multi-omics analyses will be performed on the first 300 samples to correlate outcome with cfDNA patterns, PBMC coding and non-coding mRNA expression, PBMC subpopulations and cytokine profiles (**Figure 2**). We will construct mixed effects regression models for each candidate feature. For continuous markers (cytokines) we will construct linear models. All logistic regression models will be stratified by primary composite outcome (single organ dysfunction, multiorgan dysfunction, and death). For count markers (sequencing), we will run negative binomial models. We will use the Benjamini-Hochberg procedure to control the FDR at alpha 0.05. If significant interaction effects are found after FDR adjustment, post hoc comparisons will be estimated using model contrasts and summarized with 95% confidence intervals estimated from the model. **Interpretation of Results.** Multi-omics correlations will add essential information in addition to the single omics analysis. We expect that the candidate genomic, transcriptomic, proteomic and clinical predictors will have distinct correlations within the two endpoint groups. This information can help characterize the biology of the immune response to COVID-19 and identify the most promising members for the prediction algorithm.

**Aim 1.3: WGCNA and pathway analysis. Objective.** The role of the genes involved in the inflammatory response during SARS-CoV-2 infection is unclear. To better understand co-expression of genes and their biological role in patients with symptomatic COVID-19, we will perform WGCNA and pathway analysis. To dissect the pro- and anti-inflammatory responses during SARS-CoV-2 infection with a non-supervised strategy, we will use WGCNA(170). WGCNA provides a non-supervised systematic method to identify co-expressed genes and pathways linked to the primary outcome. **Bioinformatics.** Normalized transcriptome data from the first 300 samples will be stratified by composite endpoint, batch effect corrected by ComBat and filtered by variance and entropy criteria to remove uninformative transcripts (**Figure 2**)(164-166, 169). This approach offers a powerful way to reduce dimensionality while enhancing biological interpretability. The co-expressed modules and their respective eigen-genes will be interpreted in their relationship to clinical and biological features. The clinical relevance of the modules will be inferred using a linear mixed effect model. The biological relevance of the modules will be deduced using gene ontology (GOSim(171, 172)) and pathway analysis (Strand NGS (Avadis)). **Interpretation of Results.** The results from WGCNA will offer a useful framework for relational and mechanistic reasoning. Our model will provide an integrative representation of leukocyte biology and related pathways during the COVID-19 inflammatory response. We anticipate that this strategy will enhance identification of candidate entities for the development of the prediction algorithm for adverse COVID-19 short- and long-term outcome events in Aim 2.

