
**Inflammatory Responses, COVID-19 and Clinical Organ Dysfunction.** SARS-CoV-2 infection causes major changes to the host immune system. Although inflammation is necessary to fight infection, exaggerated inflammatory responses in symptomatic COVID-19 may lead to unfavorable short- and long-term outcomes, such as new onset or worsening of frailty, organ dysfunction and death. Like other viral respiratory tract infections, SARS-CoV-2 can cause pneumonia and acute respiratory distress syndrome(44, 45), but also injury and *clinical level dysfunction in virtually every organ* system, including the cardiovascular(46-49), neurological(10, 50-52), renal(53, 54), hepatic(55-57), gastro-intestinal(58, 59), clotting(10) and immune systems(58).

**Organ dysfunction and Cytokine Storm Syndrome.** Organ dysfunction is linked to severity of sepsis(60). A subset of patients with SARS-CoV-2 infection develop profound inflammation and multi-organ dysfunction(61-63). Symptomatic COVID-19 may result in “*cytokine storm*”(64, 65), which is characterized by excessive release of pro-inflammatory cytokines and may accelerate multi-organ failure(65-71). Interleukin (IL) 1 $\beta$  and macrophage colony-stimulating factor (M-CSF) have been identified as candidate target genes for inflammatory storm(72). IL-6, IL-12, and C-reactive protein are important modulators of inflammation and may play key roles in the progression of COVID-19(61, 73). Elevated levels of pro-inflammatory ferritin and IL-6 have been identified as potential markers for fatality in COVID-19 patients(65, 67).

**Circulating Cell-Free DNA (cfDNA).** Release of mitochondrial DNA via organ-failure-related cell necrosis into the circulation may result in severe immune consequences, such as hyper-inflammation(74, 75). The spleen, liver and kidneys are responsible for eliminating circulating DNA and are often damaged in critical illness conditions, such as severe COVID-19(75-77). Thus, inflammation may be triggered not only by viral infection, but also by elevated cfDNA. During infection with SARS-CoV-2, high levels of cfDNA, composed of nuclear and mitochondrial DNA, can be produced and may induce cytokine storm and vascular abnormalities(70). cfDNA levels are associated with COVID-19 progression and severity including intubation and death (78, 79).

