**Data Collection.** The data collection method is simple, cost-effective, and minimally invasive, requiring *only one research blood draw at enrollment*, abstraction of clinical parameters from the electronic medical record, and a brief interview at enrollment, at discharge, and at one year. **Clinical Data.** Demographics, laboratory values, organ function parameters, frailty parameters, comorbidities, disability data as well as COVID-19 treatment data will be collected. **Table 1** summarizes the *routine clinical laboratory values* to be collected. Validated *organ function scores*, such as SOFA score, MELD-XI score, the Seattle Heart Failure Model will be calculated(105-107). *Comorbidities* will be assessed using Charlson and Elixhauser scoring systems(108, 109). Risk of alcohol use disorders will be assessed with AUDIT-C (110). *National Health Service Frailty Scale* scores will be assessed(111). All clinical data will be collected at baseline, at discharge and at one year after COVID-19 enrollment, abstracted into REDCap, and later analyzed using R (Vienna, AU). All patients will be interviewed in person (if not available, then by televisit) at discharge and one year after enrollment. *The National Death Index* will be searched for subjects who are uncontactable(112). **Blood Collection and Processing.** Research blood will be collected within 72h of admission and COVID-19 diagnosis confirmation and processed within 2h of sampling, into one 8 ml CPT tube (BD Biosciences) for PBMC transcriptomic analysis and cfDNA analysis and one 8 ml ACD tube (BD Biosciences) for immunophenotyping and cytokine concentration analysis. Each study site will isolate plasma and PBMC using standard procedures, aliquot these samples in duplicates and store samples at -80°C. Samples will be shipped in batches to UCLA on dry ice by express delivery. **cfDNA Sequencing.** The Illumina NovaSeq platform will be used to sequence paired-end reads of cfDNA for 2x150 bp with 1% Phix control using S4 flow cell. For cfDNA concentration quantification, we will use Invitrogen Qubit™ dsDNA HS Assay Kit and Invitrogen Qubit 2.0 Fluorometer. Then, cfDNA sequencing will be done on an Illumina HiSeq 3000. **RNA Sequencing.** Total RNA will be isolated from PBMC(25)(90). Purified RNA quality will be verified on an Agilent 2100 Bioanalyzer. RNA concentrations will be determined using a NanoDrop ND-1000 spectrophotometer. The mRNA library will be prepared with Illumina TruSeq RNA kit. The cDNA libraries will be quantitated using Qubit. Total mRNA will be amplified and sequenced on the whole-genome Illumina HiSeq 3000. **Flow Cytometry.** Immunophenotyping of PBMCs will be performed with 12-color monoclonal antibody panels to identify the subpopulations listed in **Table 2**. Cell fluorescence will be acquired on an LSR Fortessa™ cell analyzer, using standard acquisition templates. **Cytokine Quantification.** We will quantify plasma cytokine levels using a 38 multiplex Luminex array. Fluorescence intensity is acquired using a Luminex 200 instrument and xPONENT software.

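### The cf-mtDNA marker is a per-sample fragment count with no stated scaling to sequencing depth or input, and two sequencers are named for the same cfDNA assay

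*Protocol*

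**What the plan says.** Aim 1.1, Genomic Analysis, aligns the cfDNA reads, names ComBat for batch effects, and then gives the derived quantity: "We will calculate the number of cf-mtDNA fragments in each sample". It names no denominator, whether total reads, library input, plasma volume or a spike-in. The Transcriptomic Analysis text that follows lists DESeq normalisation and ComBat as two separate steps.

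Aim 1.2, Bioinformatics, sets the model: "For count markers (sequencing), we will run negative binomial models". It mentions no offset or exposure term.

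The rationale, under Circulating Cell-Free DNA in the Significance section, is about circulating amounts: "cfDNA levels are associated with COVID-19 progression and severity including intubation and death".

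In the Research Plan (Data Collection, cfDNA Sequencing), the laboratory description opens with "The Illumina NovaSeq platform will be used to sequence paired-end reads of cfDNA", on an S4 flow cell. After a sentence on measuring cfDNA concentration by Qubit, it continues: "Then, cfDNA sequencing will be done on an Illumina HiSeq 3000". No rule assigns samples to one machine or the other, and the Qubit value is not connected to the fragment count anywhere.

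**The concern.** A fragment count depends on how much mitochondrial cfDNA was in the blood, but also on how much material went into the library and how deeply that library was sequenced. The last two are laboratory quantities. If they vary between samples, three things follow.

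- The association between the marker and outcome is diluted.
- If depth or input happens to differ between endpoint-positive and endpoint-negative patients, the count can show a difference that is not biological.
- A coefficient estimated on counts at one depth does not carry over to samples sequenced at another. This matters if the marker passes screening into the Aim 2 model, which is to be validated on 200 further patients and released as a web tool.

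The two sequencer statements add to the uncertainty, because the reader cannot tell which platform produces the counts.

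**Working it through.** **No plan figure to reproduce.** No sample size, power or AUC figure in the Protocol depends on this marker. The check is a reading of the text, followed by an illustration whose variance inputs are all assumptions. The Protocol gives no read depth, library input or marker SD.

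**Step 1: what the count contains.** For sample i, write the expected count as

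E[Mᵢ] = (mitochondrial level)ᵢ × (input factor)ᵢ × (depth factor)ᵢ.

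On the log scale the three terms add. ComBat adjusts differences between batches. The Protocol plans 5 batches of about 120 samples, and variation in depth or input among samples inside one batch remains after that adjustment. ComBat is also mentioned before the count is formed, so it is not clear that it is applied to the count at all.

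**Step 2: share of variance that is signal.** With independent log-scale variation, share = s_bio² / (s_bio² + s_depth²). Assume s_bio = 0.8:

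| Within-batch depth log-SD | Calculation | Share |
|---|---|---|
| 0.3 | 0.64 / (0.64 + 0.09) | 0.88 |
| 0.5 | 0.64 / (0.64 + 0.25) | 0.72 |
| 0.7 | 0.64 / (0.64 + 0.49) | 0.57 |

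Varying the biological SD as well widens the range. With 0.6 and depth 0.7 the share is 0.36 / 0.85 = 0.42. With 1.0 and depth 0.3 it is 1 / 1.09 = 0.92.

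**Step 3: simulated effect on a comparison.** The set-up was 300 patients (60 endpoint positive, 240 negative, as in Aim 1.2), a Mann-Whitney test at two-sided 0.05, and 1000 runs. It assumed a true 1.5-fold difference, s_bio = 0.8, and three batches of 100 with one sequenced three times as deeply. ComBat was approximated by centring each batch. The normalised comparator removes the depth/input factor exactly, so it is a best case.

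| Within-batch depth/input log-SD | Power, count after batch centring | Power, normalised |
|---|---|---|
| 0.2 | 0.91 | 0.92 |
| 0.5 | 0.83 | 0.93 |
| 1.0 | 0.56 | 0.92 |

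With no true difference and a depth/input log-SD of 0.3, the proportion of runs declared significant was:

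| Depth/input ratio between outcome groups | Count | Normalised |
|---|---|---|
| 1.0 | 6% | 6% |
| 1.2 | 28% | 4% |
| 1.5 | 87% | 5% |

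The false signal needs a depth or input imbalance by outcome. Without one, the count only loses power.

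**Step 4: which scaling estimates what.** Let T be total mapped fragments, Q the Qubit cfDNA concentration per mL plasma, and M the mitochondrial fragments.

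- M / T is the mitochondrial fraction. In a negative binomial model for M, the offset log(T) targets the same quantity.
- (M / T) × Q is a circulating mitochondrial concentration. Calling it c, E[M] = T × c / Q, so the matching offset is log(T) − log(Q).

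These are different quantities. An offset of log(T) alone does not give a concentration.

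**Step 5: the sequencers.** The two statements stand in one paragraph and concern one assay. They cannot both describe a single-platform assay, and nothing describes a split.

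**The case against.** The strongest reply is that the text is silent on scaling and does not rule it out. It does not say the count will be analysed unscaled, and an offset or library-size adjustment is the kind of detail a statistical analysis plan may supply. That plan is not at hand. This is fair as far as it goes, and it limits the finding to what the Protocol fixes. But the Protocol does name the derived measure, and for RNA it lists normalisation as a step distinct from ComBat. Plasma input volume and the choice of sequencer are also laboratory matters, which a later analysis plan cannot restore.

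Several stronger readings are tempting and should not be drawn.

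- A reader might infer that the study rests on a cfDNA concentration effect. The Preliminary Data section puts transcriptomic and clinical markers first and lists cfDNA among additional parameters that may help.
- A reader might infer that concentration is lost altogether. Qubit measures total cfDNA, and the group's earlier exercise study analysed total cfDNA alongside the mitochondrial fragments. The Protocol simply does not tie the Qubit value to the Aim 1.1 marker.
- A reader might argue that a patient with far more circulating cfDNA would give the same count. That requires equal-mass library loading, on which the Protocol says nothing.
- A reader might conclude that samples will be divided between two machines, or that the final algorithm will fail to transfer. No split is stated, and if platform coincided with batch, ComBat could absorb a mean shift. A weight for this marker exists only if it passes screening and LASSO selection.

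**Conclusion.** The point holds in a limited form. Followed as written, the cf-mtDNA marker carries within-batch depth and input variation that the named batch correction does not remove. This costs precision, allows bias if depth or input is related to outcome, and hinders transfer of any coefficient. The conflict between the two sequencer statements is plain from the text and needs no assumption.

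The size of the loss cannot be established from the documents. The signal share of about 0.88 to 0.57, and the wider 0.92 to 0.42, follow from assumed SDs and run from minor to serious. They illustrate the mechanism and should not be read as estimates for this study. One add-on component of a multi-omic predictor is affected, and no stated power or precision figure changes. The correction is worthwhile because it is cheap and uses quantities the assay mostly produces already.

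**What to change.** 1. In Aim 1.1, Genomic Analysis, define the marker as mitochondrial fragments divided by total mapped fragments. Analyse Qubit total cfDNA per mL plasma as a separate marker, and record the plasma input volume for every sample. If circulating cf-mtDNA level is the target, use the product of the two.
2. In the Aim 1.2 negative binomial model for this count, use the offset log(total mapped fragments) for the fraction, or log(total mapped fragments) − log(Qubit ng/mL) for the concentration, so that model and marker estimate the same quantity.
3. In the Research Plan, reconcile the two sequencer statements. Use one platform for all cfDNA samples, or include platform as a batch factor if both are used.

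The cost is a few sentences, one recorded volume per sample and a line of code; read totals and Qubit values come from the assay as described. The plasma volume has to be recorded when samples are processed. A small downside is that Qubit measurement error enters the concentration marker.
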